#### Sensitivity analyses

Sensitivity analyses will be conducted to examine whether the pattern of results from the main analyses differ after excluding participants guessing the aims of the study.

We will also repeat the main analysis substituting the categorical variable *highest educational qualification* by the composite variable *level of education* as a continuous covariate.

We will report whether sensitivity analyses result in deviations from the pattern of significance to the main analyses (i.e., any significant differences between conditions becoming not significant, and vice versa).

[figure not shown]

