- They may be on the individual sign adjacent to the food itself, or on a separate, larger sign in close proximity to the food. The customer must be able to easily read the sign when making a selection.

In the no energy labelling conditions (C and A) there will be no kcal information next to menu options.

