## 6. STUDY FLOW

RECRUITMENT (Prolific)	
 
▪ Predefined screening questions of Prolific website will be used to target the sample (Appendix C)
 
▪ Participants who meet the inclusion/exclusion criteria will be emailed by Prolific and/or offered to complete our study on their Prolific account (Appendix D)
 
▪ Eligible participants who want to take part on the study will click on the start button and be redirected to our study website (Qualtrics)
 

INFORMED CONSENT	
 
▪ Participants will read the information sheet (Appendix E)
 
▪ Participants who want to proceed will tick a consent box (Appendix F)
 

RANDOMISATION	
 
▪ When starting the study, participants will be equally randomized to the four experimental conditions
 

BASELINE ASSESSMENTS	
 
▪ Participants will complete a baseline questionnaire on demographics (Appendix G)
 

MEAL CHOICE TASK	
 
▪ Instructions will be displayed (Appendix H)
 
▪ Dining-out scenarios will be displayed in randomised order
 
▪ For each dining out scenario, participants will be asked to choose their main meal and whether they would like to order a side and a dessert.
 

	Control condition	Energy labelling condition	Low energy increased availability condition	Low energy increased availability and energy labelling condition
HEALTH MOTIVATION	▪ Single-item Food Choice Questionnaire ( Appendix I )			
DEBRIEFING	▪ Aim guessing in an open-ended response format ▪ Insight on the participants' perception of the meal ordering task ( Appendix J ) ▪ Text to tell the participants what the study was about ( Appendix K )			
DATA MANAGEMENT	▪ The result files will contain: ○ Participant unique ID ○ Experimental condition participant is directed to ○ Food choices ○ Answers to questionnaires			

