## 7. STATISTICAL ANALYSIS

All statistical analyses will be performed using SAS version 9.3 (SAS Institute, Inc., 2012 SAS® 9.3. Cary, NC). The level of significance will be set at  $p < 0.05$ . Linear mixed models will be fitted with PROC MIXED.

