### Other variables

**Household income:** To be consistent with US census data [35], participants will report their annual household income before tax to the nearest \$1000.

**Subjective SES:** The measure of the Subjective Social Status using the MacArthur Scale will be coded from 1 to 10.

**BMI** will be calculated as weight (kg) / Height ( $m^2$ ). BMI data only will be trimmed for implausible values:  $BMI > 10$  or  $BMI < 60$  [36].

**Aim guessing:** Participants who identify the aim of the study as being to examine the influence of energy labelling or increased availability of lower energy food items on food choices will be coded as

being aware of the study aims. Responses will be independently coded by two researchers, with discrepancies in coding decisions resolved by a third researcher.

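### Sensitivity analyses are compared with the main analysis only by whether significance at 0.05 changes, which can mislead in both directions when aim guessers are excluded

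*Combined protocol and SAP*

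**What the plan says.** Section 7.4 (Sensitivity analyses) plans two checks. The first asks whether results "differ after excluding participants guessing the aims of the study". The second repeats the main model with a continuous education composite in place of the binary education variable. For both, the stated comparison is the pattern of significance: "We will report whether sensitivity analyses result in deviations from the pattern of significance to the main analyses", spelled out as "any significant differences between conditions becoming not significant, and vice versa". The section does not ask for estimates or confidence intervals to be compared, and it does not say how large a change would matter.

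The level is 0.05: Section 7 states "The level of significance will be set at" p < 0.05. The 0.01 level at the end of Section 7.5 is for secondary analyses, and these checks sit under 7.4.

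Section 7.2 (Other variables) defines who is excluded: "Participants who identify the aim of the study as being to examine the influence of energy labelling or increased availability" of lower energy items are coded as aware. Naming either intervention is enough, in any arm. Section 6 places this question at debriefing, after the meal task: "Aim guessing in an open-ended response format". Section 5.1 (Interventions) says "In the no energy labelling conditions (C and A) there will be no kcal information next to menu options". No section gives an expected guess rate, overall or by arm. The allowance of about 20% in Section 7.6 covers dropouts and failed quality controls only.

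**The concern.** A change of significance mixes two things: a change in the estimate and a change in its standard error. Excluding aim guessers always does the second, so a deviation can appear when the effect has not moved. It can also fail to appear when the effect has moved a great deal but both p-values stay on the same side of 0.05.

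The aim-guesser analysis exists to show whether a labelling or availability effect is partly a response to perceived study demands. A reader needs to know how much of the effect remains without the guessers, and the stated criterion does not answer that.

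There is a second issue. Guessing is recorded after exposure to the assigned menus. If it is more common in some arms than others, the reduced comparison is open to post-randomisation selection. A changed result could then reflect selection, lost precision or demand effects, and a change in significance cannot tell these apart.

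**Working it through.** **Inputs.** From Section 7.6: 1,000 analysed, 6 orders each, variance 47,244 at each level, unlabelled mean 706 kcal, expected labelling reduction 7%. From Section 6: equal allocation to four arms, so 500 v 500 for each factor. Two-sided 0.05 is assumed, because sidedness is not stated. The exclusion rate is assumed, because none is given.

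**Standard error, full sample.** Variance of a participant's mean = 47,244 + 47,244/6 = 55,118. SE = √(55,118 × 2/500) = 14.85 kcal.

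**The plan's own power figure.** Section 7.6 states 0.93 for a 2% reduction. 2% of 706 = 14.1 kcal, so z = 14.1/14.85 = 0.95 and power is 0.16. The stated figure is not reproduced. The software settings are not given, so the cause cannot be identified, and this is a separate matter. At the expected 7%, 0.07 × 706 = 49.4 kcal, z = 49.4/14.85 = 3.33 and power is 0.914. The 7% case is used below, together with a test at the plan's stated 0.81.

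**Significance lost with the effect unchanged.** With a fraction f retained at random, the SE becomes 14.85/√f. The retained sample is nested in the full one, so its estimate equals the full estimate plus independent noise of variance SE²(1/f − 1). Simulating the pair (1 to 2 million draws) gives the share of significant main results that become non-significant:

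| Excluded at random | Power after exclusion, 7% effect | Significance lost, 7% effect | Significance lost, test with 0.81 power |
|---|---|---|---|
| 5% | 0.900 | 2.5% | 4.5% |
| 10% | 0.884 | 4.4% | 7.7% |
| 20% | 0.845 | 8.8% | 14% |

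**Does concentration in the labelled arms matter?** At the same total loss of 200, excluding 20% of both groups gives 8.8%, and excluding 10% of unlabelled and 30% of labelled participants gives 9.4% (7% effect). For precision, total loss matters more than where it falls. Concentration matters mainly through selection, which this arithmetic does not measure.

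**A real change that is missed.** With 20% excluded (400 v 400), SE = √(55,118 × 2/400) = 16.60 kcal, and the limit of significance is 1.96 × 16.60 = 32.5 kcal. A main estimate of 70 kcal (z = 70/14.85 = 4.71) could fall to 33 kcal and remain significant. Under random exclusion the SE of the change is √(16.60² − 14.85²) = 7.42 kcal, so a fall of 37 kcal is 37/7.42 = 5.0 standard errors, far beyond sampling noise. This is close to the limiting case: it implies an effect of about (70 − 0.8 × 33)/0.2 = 218 kcal among the guessers. A milder fall, from 49.4 to 35 kcal (14.4 kcal, or 29% of the effect), would also pass as no deviation.

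**The case against.** The best defence is that Section 7.4 commits only to reporting deviations. It attaches no conclusion to them and does not let a sensitivity result replace the main one. Its opening sentence speaks more broadly of the pattern of results, and nothing prevents the authors from showing estimates and intervals. The main estimate and inference are unaffected. All of this stands, and it limits the weight of the point. It does not remove it, because change of significance is the only comparison the plan defines.

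Three stronger readings are tempting, and the documents do not support them.

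- **That the exclusion falls mainly on the labelled arms.** More guessing there is plausible, since only those arms show kcal. But no rate is given, guesses about availability also count, and every arm answers items on healthiness and weight control before the aim question.
- **That results will be called non-robust.** The plan never says so.
- **That a quarter to a third of significant results would be lost.** The simulation does give 23% (10% excluded) and 35% (20% excluded), but only if the true effect is 2%. Recomputed power is then 0.16, so these are shares of the few trials that reach significance. The plan expects 7% for labelling.

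The sample-loss argument also does not reach the education-composite analysis, which excludes nobody. There the objection is only that significance alone is an inadequate comparison.

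**Conclusion.** The point holds as a weakness in a stated reporting criterion. For the aim-guesser exclusion, loss of sample alone would turn about 2.5% to 9% of significant labelling results non-significant at the expected 7% effect, and about 5% to 14% for a test with power near 0.81. In the other direction, at 20% exclusion the criterion would miss a fall from 70 to 33 kcal.

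These figures assume 5% to 20% excluded at random, the plan's variances, 500 v 500 and a two-sided test. The exclusion rates are assumptions. Selection through different guess rates by arm is a risk that cannot be sized from the documents. The consequence is a poorly informative check on demand effects; the primary result itself is not wrong.

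**What to change.** In Section 7.4, replace the significance-pattern criterion with a side-by-side report of main and sensitivity estimates, 95% CIs and the change in kcal, for labelling, availability and their interactions. Say that the sensitivity analyses will be interpreted on those quantities.

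For the aim-guesser analysis, report the number excluded in each of the four arms, and state that the reduced comparison is not protected by randomisation.

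For the education-composite analysis, compare the labelling and availability effects in kcal. Binary and z-scored education interactions are on different scales, so compare them only after putting them on a common one, for example the predicted intervention effects at the mean composite score of the lower and the higher education groups.

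The cost is a change of wording and slightly more reporting. The models are those already planned.

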### 7.5. Secondary analyses

#### Moderated mediation analysis of health motivation

[figure not shown]
If the main analyses suggest that *highest educational qualification* moderates the effect of *labelling* or *availability* on *energy of the main* (i.e., the *labelling\* highest educational qualification* or *availability\* highest educational qualification* interaction is significant), moderated mediation analyses will be performed in order to examine the extent to which health motivation (HM) (healthiness motivation and weight control motivation) mediates the effect of *highest educational qualification* on *energy of the main* with and without labelling.

If the main analysis reveals any significant interactions between *labelling* or *availability* and *familiarity*, then repeated ordering will be aggregated at participant level by calculating the average energy of the mains for familiar and unfamiliar cuisines separately. If the main analysis reveals no interaction between *labelling* or *availability* and *familiarity*, then repeated ordering will be aggregated at participant level by calculating the average energy of the mains for all cuisines.

Conceptual diagram example (labelling):

Statistical diagram example (labelling):

Conditional indirect effect of *highest educational qualification* on the *average energy of the mains* through *HM* =  $a(b_1 + b_2)$  *labelling*.

The moderated mediation will be tested by estimating the conditional indirect effect of *level of education* on the *energy of the main* through *HM* for *labelling* and *no labelling* conditions (resp. the *increased* and *baseline availability* conditions) and testing the conditional indirect effect for those conditions using bias-corrected bootstrap. We will use the PROCESS macro (Model 15) on SAS version 9.3 that provides asymmetric bias-corrected bootstrap confidence intervals for inference about the conditional indirect effects using 5,000 bootstrap samples [38]. Moderated mediation will be tested by determining whether or not the confidence intervals contain zero.

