## 2. OBJECTIVES, OUTCOMES MEASURES AND HYPOTHESES

OBJECTIVES	OUTCOME MEASURES	HYPOTHESES
Primary objective  To examine the effect that an information-based intervention (energy labelling)	Energy (kcal) of the ordered meal.	An increased availability of lower energy menu options will result in a decrease in total

and a structural intervention (increased availability of lower kcals options) have on kcals ordered in a hypothetical meal ordering task among participants of lower and higher SES.
		
energy ordered among both participants of lower and higher SES. However, energy labelling may exert a stronger effect on energy ordered among participants of higher vs. lower SES.

Secondary objectives
 
To examine the reasons why the effects that energy labelling have on kcals ordered may vary based on a participants' SES.
 
To examine the effect of labelling on familiar and unfamiliar cuisines menus.
	
Health motivation in food choices (questionnaire score).
 
Energy (kcal) of the ordered meals for familiar and unfamiliar cuisines.
	
The participants of higher SES will be more motivated by health in their food choices than participants of lower SES, which will mediate the relationship between SES and the effect of energy labelling on the total energy ordered.
 
Energy labelling will have a greater effect for unfamiliar compared to familiar cuisines.

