### 7.4. Main analyses

The measure of SES used in our primary analysis will be the *highest educational qualification* (categorical variable: *lower vs. higher*) because previous research showed that people with college education were more likely to use kcal labels at restaurants [37]. The measure of health motivation will be the response to the first item from the Single-item Food choice Questionnaire: “It is important to me that the food I eat on a typical day is healthy”, i.e., importance of healthiness.

First, we will examine whether our manipulation of familiarity is valid by examining the proportion of participants that are familiar / unfamiliar with each cuisine menu type (i.e. we expect >75% of participants to be familiar with our chosen ‘familiar’ cuisines and <25% of participants to be familiar with our ‘unfamiliar’ cuisines). We will also report the mean and SD of the *familiarity score* for each cuisine.

A linear mixed model will be used to test the effect of *labelling* (categorical, between-subject), *availability* (categorical, between-subject), *highest educational qualification* (categorical, between-subject), *familiarity* (categorical, within-subject) and *labelling\*highest educational qualification*, *availability\*highest educational qualification*, *labelling\*familiarity*, *availability\*familiarity*, interactions on *energy of the main* for the six dining out scenario. A random effect of participant will be added by using an unstructured covariance structure to account for correlation between repeated ordering by the same participant.

If any interactions with *familiarity* are significant, analysis will be stratified by *familiarity* and two linear mixed models will be fitted to examine the effect of *labelling*, *availability*, *highest educational qualification* and *labelling\*highest educational qualification*, *availability\* highest educational qualification* interactions on *energy of the main* for familiar and unfamiliar cuisines with participant effect as random to account for correlation between repeated ordering by the same participant for familiar and unfamiliar cuisines.

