#### Debriefing questionnaire

We will finally explore whether the restaurants menus are valid and the extent to which participants reported using kcal information when making food choices. Responses to the debriefing questionnaire will be analysed:

- We will describe the responses to each item (mean, SD, % agree [5, 6, 7], % disagree [1, 2, 3]) in the overall sample to characterise *validity of menu design, validity of food offer, kcal influence*.
- Three linear mixed models will be used to test the effect of *labelling, availability, familiarity* and *highest educational level* on the three dimensions of the debriefing questionnaire (a) *validity of menu design*, (b) *validity of food offer*, and (c) *kcal influence* to investigate whether the responses differ across experimental conditions and SES.

To account for multiple testing the alpha level for secondary analyses will be set at  $p = 0.01$ .

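### Section 7.5's rule for moderated mediation checks each condition's indirect effect against zero but never tests whether the two indirect effects differ

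*Combined protocol and SAP*

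**What the plan says.** Section 2 gives the hypothesis. Participants of higher SES are expected to be more motivated by health, "which will mediate the relationship between SES and the effect of energy labelling on the total energy ordered".

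Section 7.5 (Moderated mediation analysis of health motivation) is entered only if the main model shows a significant education interaction with labelling or availability. Its stated aim is the extent to which health motivation "mediates the effect of *highest educational qualification* on *energy of the main* with and without labelling". It fits PROCESS Model 15 with 5,000 bootstrap samples, estimates the indirect effect separately in the two conditions, and proposes "testing the conditional indirect effect for those conditions using bias-corrected bootstrap". The decision rule is: "Moderated mediation will be tested by determining whether or not the confidence intervals contain zero".

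The intervals are described only as being for the conditional indirect effects. Neither section 7.5 nor any other section gives an interval or test for the difference between them. The mediation text states no confidence level, but section 7.5 ends: "To account for multiple testing the alpha level for secondary analyses will be set at" p = 0.01.

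Section 7.6 supports the analysis with a cited sample of about 380 for 0.8 power to detect a mediated effect.

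**The concern.** Moderated mediation means that the indirect effect changes with the moderator. Reading the plan's formula as a(b1 + b2 × labelling), the indirect effect is a × b1 without labels and a(b1 + b2) with them, so the difference is a × b2. Two intervals that both exclude zero show mediation in each condition. One that excludes zero beside one that does not is not evidence of a difference either. The rule does not say which of these patterns counts.

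At stake is the first secondary objective, which is to explain why the labelling effect varies by SES. The rule could credit health motivation with an interaction it plays no part in, or miss moderation that is real.

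**Working it through.** **The plan's own figure.** With section 7.6's correlations (education to motivation 0.17, motivation to kcal -0.25) and n = 380, the power for both paths to be significant is Φ(atanh(0.17) × √377 − 1.96) × Φ(atanh(0.25) × √377 − 1.96) = 0.914. A bias-corrected bootstrap simulation gives 0.95. So 380 is enough on those inputs, but for one indirect effect, not for a difference between two.

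**Inputs.**
- N = 1,000 (7.6), split 500/500 by condition (equal randomisation, section 6).
- 60% higher education: 30 + 20 + 10% (4.1, with the coding in 7.2).
- a = 0.17 and b = -0.25 (7.6). Treating these correlations as paths is an assumption, and all other b values are assumed.
- Variance 47,244 at each level, six menus (7.6).

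**How often the gate opens when b2 = 0.** The SD of a participant's mean is √(47,244 + 47,244/6) = 234.8 kcal. The SE of the education × condition interaction is 234.8 × √(1/(1,000 × 0.24 × 0.25)) = 30.3 kcal. For a direct-path interaction δ, the gate rate is Φ(δ/30.3 − 1.96) + Φ(−δ/30.3 − 1.96). The Appendix A American baseline menu averages 9,730/10 = 973 kcal.

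| Direct-path interaction | Gate, formula | Gate, simulated | Gate and both 99% intervals exclude zero | Gate and 99% percentile interval for a × b2 excludes zero |
|---|---|---|---|---|
| 0 | 5.0% | 5.2% | 5.2% | 0.10% |
| 14.1 kcal (2% of 706) | 7.5% | 7.5% | 7.5% | 0.05% |
| 19.5 kcal (2% of 973) | 9.8% | 9.4% | 9.4% | 0.13% |
| 47 kcal (the labelling effect cited in 7.6, all in one education group) | 34.1% | 32.0% | 32.0% | 0.25% |

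The simulations used b = -0.25 in both conditions, 2,000 to 4,000 trials per row and 5,000 resamples. Columns three and four agree because both intervals exclude zero in about 100% of trials. The last column uses percentile intervals. With the planned bias-corrected method, the 99% interval for a × b2 rejects in about 1.6% of null trials before the gate, which caps the joint rate.

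**Exactly one interval excludes zero.**
- Equal paths of -0.25: about 0% false signals before the gate.
- Equal paths of -0.10: about 45% before the gate (46% with 95% and 45% with 99% intervals; 300 trials, Monte Carlo error up to about 3 points).
- Real moderation, b = -0.15 versus -0.35 (2,000 trials): detected in 7% (95%) or 19% (99%), against 92% or 78% for bias-corrected a × b2. A smaller run gave 6% and 19% against 90% and 78%.

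**Power of a × b2 at 99%, bias-corrected, before the gate.** 78% for b = -0.15 versus -0.35, and 19% for -0.20 versus -0.30. If moderation runs only through motivation, the first case shifts the interaction by 0.17 × 0.20/√0.24 × 234.8 = 16.3 kcal, for which the formula gives a gate rate of about 8%. The simulated gate rates are 9% and 6%.

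**The case against.** **The aim is descriptive.** The separate intervals do suit the aim of describing mediation with and without labelling, and that part stands. But the same text presents the rule as a test of moderated mediation, and the section 2 hypothesis concerns the difference.

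**The gate already shows moderation.** It shows that the effect on energy is moderated, not that the path through motivation is. Model 15 as simulated lets the direct path vary too.

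**A reader might infer that the rule credits motivation almost automatically once the gate opens.** The documents do not support that. It holds near b = -0.25 if both intervals must exclude zero. With b = -0.10 in both conditions, both 95% intervals exclude zero in 41% of trials; with b = -0.05, in 4%. The -0.25 is a correlation with kcal ordered in a previous virtual fast-food trial, not a path to energy of the main in this one. If exactly one interval must exclude zero, the false-claim rate at -0.25 is about nil.

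**A reader might want further changes.** The documents do not require them:
- Replacing the bias-corrected interval with a percentile one is a preference.
- No single deciding contrast is dictated: section 7.2 scores both the healthiness and weight-control items, section 7.4 names the first, and section 7.5 uses both.
- The bracket in the printed formula may be an extraction artefact.

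**The gain in power is small.** This stands. With the gate kept, the chance of declaring moderation that runs only through motivation cannot exceed the gate rate, which is under 10% in the cases examined.

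**Conclusion.** The point holds. As written, the rule is not a test of moderated mediation under any reading of which intervals must exclude zero, and the gate does not make it one. The size of the error rests on the assumed paths and the reading:
- Both must exclude zero, equal paths of -0.25: the false-claim rate equals the gate rate, which is 5% with no interaction, about 7.5-10% for a 2% direct-path interaction and about 34% at 47 kcal.
- Exactly one must exclude zero: about 45% false signals before the gate at equal paths of -0.10, and most of the real moderation at -0.15 versus -0.35 is missed.

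This is a gated secondary analysis. It would be wrong to infer that the primary results are in doubt, because the main model does not use this rule. The change is worth making, since this analysis is the one planned to address the first secondary objective. Its main benefit is to prevent false claims.

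**What to change.** Replace the last sentence of the moderated mediation text in section 7.5 with: *Moderated mediation will be declared only if the bias-corrected bootstrap 99% confidence interval for the difference between the two conditional indirect effects (a × b2) excludes zero; the conditional indirect effects in each condition will be reported descriptively.* This keeps the planned bootstrap and applies the plan's own 0.01 level for secondary analyses.

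The cost is one sentence and one contrast from the same bootstrap draws. Whether the cited PROCESS version prints that contrast cannot be checked from the documents; if it does not, a few lines of SAS will. The downside is lower power than for simple mediation, as shown in the working.

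Two minor and separate corrections in section 7.6: 1,000 participants equally randomised give 1,000/2 = 500 per labelling or availability condition, not 580; and the adequate-power statement should be limited to simple mediation within a condition, for which 500 still exceeds the cited 380.
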